8.2 Methods and Timing for Assessing, Recording, and Analyzing Safety Parameters

The Schedule of Study Procedures is located in [Appendix 1](#).

TEAEs will be recorded in source documents and on Grifols form for recording of TEAEs.

8.3 Procedures for Eliciting Reports of and for Recording and Reporting Adverse Event and Intercurrent Illnesses

8.3.1 Warnings/Precautions

True hypersensitivity reactions from IVIG administration are rare. They can occur in subjects with anti-IgA antibodies. Rarely, human normal immunoglobulin can induce a fall in blood pressure with anaphylactic reaction, even in subjects who had tolerated previous treatment with human normal immunoglobulin.

There is clinical evidence of an association between IVIG administration and thromboembolic events such as myocardial infarction, cerebral vascular accident (including stroke), PE, and DVT that is assumed to be related to a relative increase in blood viscosity through the high influx of immunoglobulin in at-risk subjects. In subjects at risk for thromboembolic adverse reactions, IVIG products should be administered at the minimum rate of infusion and dose practicable.

Cases of acute renal failure have been reported in subjects receiving IVIG therapy. In most cases, risk factors have been identified, such as pre-existing renal insufficiency, diabetes mellitus, hypovolemia, overweight, concomitant nephrotoxic medicinal products, or age over 65. In case of renal impairment, IVIG discontinuation should be considered. While these reports of renal dysfunction and acute renal failure have been associated with the use of many of the licensed IVIG products containing various excipients such as sucrose, glucose, and maltose, those containing sucrose as a stabilizer accounted for a disproportionate share of the total number. In subjects at risk, the use of IVIG products that do not contain these excipients may be considered. Gamunex-C *does not* contain sucrose, maltose, or glucose.

AMS has been reported to occur in association with IVIG treatment. The syndrome usually begins within several hours to 2 days following IVIG treatment.

Gamunex-C may contain blood group antibodies which may act as hemolysins and induce in vivo coating of red blood cells with immunoglobulin, causing a positive DAT and, rarely, hemolysis. Hemolytic anemia can develop subsequent to IVIG therapy due to enhanced red blood cells sequestration. IVIG recipients should be monitored for clinical signs and symptoms of hemolysis. If these are present after IVIG infusion, perform appropriate confirmatory laboratory testing.

In subjects receiving IVIG, there have been some reports of acute non-cardiogenic pulmonary oedema (Transfusion Related Acute Lung Injury [TRALI]). TRALI is characterized by severe hypoxia, dyspnoea, tachypnoea, cyanosis, fever and hypotension.

GRIFOLS Bioscience Industrial Group	Number	BLG-CL-PRT-000020	Version	4.0	Status	Effective	Effective Date	19-Jul-2021
	GC2007 - A Multicenter, Randomized, Open-label Parallel Group Pilot Study to Evaluate Safety and Efficacy of High Dose Intravenous Immune Globulin (IVIG) plus Standard Medical Treatment (SMT) versus SMT alone in						Page	57 of 91

Standard measures to prevent infections resulting from the use of medicinal products prepared from human blood or plasma include selection of donors, screening of individual donations and plasma pools for specific markers of infection and the inclusion of effective manufacturing steps for the inactivation/removal of viruses. Despite this, when medicinal products prepared from human blood or plasma are administered, the possibility of transmitting infective agents cannot be totally excluded. This also applies to unknown or emerging viruses and other pathogens. The measures taken are considered effective for enveloped viruses such as human immunodeficiency virus (HIV), hepatitis B virus (HBV) and hepatitis C virus (HCV), and for the non-enveloped hepatitis A and parvovirus B19 viruses. There is reassuring clinical experience regarding the lack of hepatitis A or parvovirus B19 transmission with immunoglobulins and it is also assumed that the antibody content makes an important contribution to viral safety. It is strongly recommended that every time that Gamunex-C is administered to a subject, the batch number of the product is recorded in order to maintain a link between the subject and the batch of the product.

8.3.2 Adverse Event Monitoring

Subjects must be carefully monitored for AEs particularly in terms of their seriousness, severity, and causal relationship to the IP.

8.3.3 Adverse Event Definitions

8.3.3.1 Adverse Events

An AE is defined as any untoward medical occurrence in a subject or clinical investigation subject administered a medicinal product or study treatment and which does not necessarily have a causal relationship with this administration. An AE can therefore be any unfavorable and unintended sign (including any abnormal laboratory finding, for example), symptom, or disease temporally associated with the use of a medicinal product, whether or not considered related to the medicinal product.

In this clinical study, disease progression is defined as the worsening of a subject's condition attributable to the disease for which the investigational product is being studied. It may be an increase in the severity of the targeted disease and/or increases in the symptoms of the targeted disease. Anticipated symptoms of COVID-19 include fever, cough, hypoxia, dyspnea, hemoptysis, myalgia, fatigue, pharyngitis, which may develop at any time during the course of the disease. The development of COVID-19 symptoms during the clinical study should not be recorded as individual TEAEs, unless there is evidence suggesting a causal relationship between IVIG and the TEAE.

8.3.3.2 Suspected Adverse Drug Reactions/Adverse Reactions

All noxious and unintended responses to a medicinal product or study treatment related to any dose should be considered suspected ADRs (i.e., potentially drug related AEs). The phrase "responses to a medicinal product" means that a causal relationship between a medicinal product or study treatment and an AE is at least a reasonable possibility.

GRIFOLS Bioscience Industrial Group	Number	BLG-CL-PRT-000020	Version	4.0	Status	Effective	Effective Date	19-Jul-2021	Page	58 of 91
	GC2007 - A Multicenter, Randomized, Open-label Parallel Group Pilot Study to Evaluate Safety and Efficacy of High Dose Intravenous Immune Globulin (IVIG) plus Standard Medical Treatment (SMT) versus SMT alone in									

In the framework of this study, a suspected ADR for which there is a reason to conclude that the drug caused the event will be labeled as an AR; thus, ARs are a subset of suspected ADRs.

8.3.4 Assessment of Causality of Adverse Event

The investigator is required to provide a causality assessment for each AE reported to the sponsor. The assessment of the causal relationship of an AE to the administration of IP must be a clinical decision based on all available information at the time of the completion of the CRF and/or SAE Report Form. The sponsor will consider the investigator's causality assessment and also provide its own assessment.

Causal relationship to the IP will be established according to medical judgment on whether there is a **reasonable possibility of a causal relationship between the AE and the IP administration.**

The investigator must determine and classify the AE causality according to the following categories:

Unrelated/Not related: there is not a reasonable possibility of causal relationship between the AE and the IP.

Possibly related: there is evidence to suggest a causal relationship between the IP and the AE.

Definitely related: there is a reason to conclude that the IP caused the AE.

Criteria to assess the causal relationship should take into account of the following conditions: 1) a plausible temporal sequence from the IP administration to the AE onset; 2) whether the event follows a known response pattern to the suspected treatment; 3) whether the AE could be reasonably explained by the subject's clinical state, comorbidities, or concomitant medications, as well as 4) the occurrence of improvement on stopping/reducing the treatment (positive dechallenge) and/or reappearance of the event on repeated exposure (positive rechallenge).

For expedited safety reporting purposes, AEs assessed as either "definitely related" or "possibly related" will be considered POTENTIALLY RELATED or just RELATED.

Any AE reported prior to the first administration of the IP will be considered a non-treatment-emergent AEs and causal relationship will always be "Unrelated/Not related."

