8.3.8 Adverse Event Documentation

All AEs and SAEs occurring on Day 1 through the Day 29 (± 1 day)/Final Visit must be fully recorded in the subject’s medical record and CRF, and SAE form (if serious).

At the time of the Day 60 (± 2 days) and Day 90 (± 2 days) Phone Checks any additional SAEs/non-serious AEs will also be collected and recorded.

It is the responsibility of the investigator to ensure that AEs are appropriately recorded.

AEs will be collected through directly observed events or spontaneously volunteered by the subject. Clearly related signs, symptoms and abnormal diagnostic procedures should preferably be grouped together and recorded as a single diagnosis or syndrome wherever possible.

The following variables must be recorded:

- The verbatim term (a diagnosis is preferred)
- Date/time of onset
- Date/time of resolution
- Severity (mild, moderate, severe [Grade 3 to Grade 5])
- Causality (unrelated, possibly related, definitely related)*
- Seriousness (yes, no)
- Action taken (with regard to IP)
- Other action (to treat the event)
- Outcome and sequel (follow-up on AE)

*Causality assessment will be made only when the AE occurs after the subject has initiated at least one infusion of the IP. An AE occurring before subject’s exposure to IP will be always labeled as “unrelated”.

GRIFOLS Bioscience Industrial Group	Number	BlG-CL-PRT-000020	Version	4.0	Status	Effective	Effective Date	19-Jul-2021	Page	61 of 91
	GC2007 - A Multicenter, Randomized, Open-label Parallel Group Pilot Study to Evaluate Safety and Efficacy of High Dose Intravenous Immune Globulin (IVIG) plus Standard Medical Treatment (SMT) versus SMT alone in									

For AEs that occur during infusions, the infusion rate in effect at the time of onset of the AE, the time of onset of the AE and the time of AE change materially in intensity and/or resolve will be captured.

In addition to the investigator's own description of the AE, each AE will be encoded according to the Medical Dictionary for Regulatory Activities (MedDRA).

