8.5 Study-Independent Safety Review Committee (SISRC) and Stopping Rules

Grifols will utilize a Study-Independent Safety Review Committee (SISRC) whose members (from Grifols) will be impartial and independent of the clinical trial team, and will consist of a statistician, global pharmacovigilance representative, and medical director. The SISRC will review relevant safety information from the study as outlined in the SISRC Charter. At a minimum, after the first 20 subjects are enrolled and have completed treatment, the SISRC will conduct an initial safety review. The SISRC will perform a causality review of all TEAEs and SAEs. The SISRC will be notified of relevant SAEs inasmuch as feasible within 24 hours, but no later than 3 days.

Stopping criteria for temporary suspension of further study enrollment/recruitment pending full safety investigation by the SISRC are detailed below.

The SISRC will conduct a safety evaluation and study enrollment/recruitment will be temporarily suspended while the safety investigation is undertaken if any one of the following occur:

- 1 death considered related to Gamunex-C
- 1 Grade 4 treatment-emergent AE occurs in any of the first 3 randomized subjects considered potentially related to Gamunex-C
- 1 subject develops a Grade 3 hypersensitivity reaction or serious anaphylactic reaction at any time attributable to Gamunex-C
- 10 subjects given Gamunex-C develop treatment-emergent AEs in the same system organ class that are \geq Grade 2 severity (CTCAE grading criteria)
- 2 subjects given Gamunex-C develop treatment-emergent Grade 4 serious AEs of the same kind in the first 10 subjects randomized to Gamunex-C
- 5 subjects develop Grade 3 or 4 treatment-emergent AEs that are at least possibly related to Gamunex-C at any time during the study
- 3 or more subjects per 10 subjects enrolled and dosed with Gamunex-C develop definitely related treatment-emergent serious AEs of the same kind (same or related verbatim terms). This stopping criterion will be applied after at least 10 subjects are randomized and treated with Gamunex-C.

GRIFOLS	Number	BLG-CL-PPR-000020	Version	4.0	Status	Effective	Effective Date	19-Jul-2021
	GC2007 - A Multicenter, Randomized, Open-label Parallel Group Pilot Study to Evaluate Safety and Efficacy of High Dose Intravenous Immune Globulin (IVIG) plus Standard Medical Treatment (SMT) versus SMT alone in Bioscience Industrial Group						Page	63 of 91

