#### 7.2.1 Treatment-emergent Adverse Events

For summary purposes, AEs will be classified as treatment-emergent AEs (TEAEs) or non-treatment-emergent AEs (non-TEAEs) depending on the comparison of AE onset date/time with the date of randomization. A TEAE will be defined as an AE which occurred on or after the date of randomization. For adverse events with incomplete start dates/times, the same imputation algorithm for missing or partial date/time information as described in Section 5.6 will be used for the determination of an AE being treatment emergent or not. Briefly, the unknown portions of an AE onset date/time will be imputed to the latest possible before being compared to the date of randomization.

Non-TEAEs will be summarized separately from TEAEs by SOC and PT for each treatment group and overall.

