## 7.2.3 Adverse Event Relationship to IP

Refer to the study protocol, Section 8.3.4.

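### Protocol and SAP start treatment-emergence at different moments and neither counts worsening, so a Day 1 pre-infusion event that worsens after IVIG can stay labelled unrelated

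*Protocol*

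**What the plan says.** Protocol 8.3.4 sets the rule for events before exposure: "Any AE reported prior to the first administration of the IP will be considered a non-treatment-emergent AEs and causal relationship will always be" unrelated. Protocol 8.3.8 repeats it by time of occurrence rather than of reporting. An event before the subject's "exposure to IP will be always labeled as" unrelated, and "Causality assessment will be made only when the AE occurs after the subject has initiated at least one infusion of the IP".

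The SAP starts elsewhere. SAP 7.2.1 states: "A TEAE will be defined as an AE which occurred on or after the date of randomization". This applies to both arms. On relatedness, SAP 7.2.3 says only "Refer to the study protocol, Section 8.3.4". SAP 7.2.5 then defines an adverse drug reaction as a TEAE rated possibly or definitely related.

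Neither document says what happens when an event begins before the first infusion and becomes more severe after it. The nearest text is in Protocol 8.3.8, for events that occur during infusions: "the time of onset of the AE and the time of AE change materially in intensity and/or resolve will be captured". That timing is not linked to treatment-emergence or to causality.

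Protocol 8.5 builds its pausing criteria on these labels, for example "5 subjects develop Grade 3 or 4 treatment-emergent AEs that are at least possibly related to Gamunex-C at any time during the study".

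**The concern.** There are two linked faults. First, the documents can classify one Day 1 event in opposite ways, and the protocol's clock cannot classify the SMT-alone arm at all, although the TEAE endpoints serve a two-arm safety objective. Second, treatment-emergence and relatedness are both decided by when an event began, with no provision for a change in severity.

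The second fault matters because Protocol 2.3.2 and 8.3.1 name pre-existing renal insufficiency as a risk factor for renal failure under IVIG, so aggravation of an existing problem is a plausible form of harm. If an event recorded before infusion worsens afterwards and stays in its first record, it is unrelated by rule rather than by judgement. At stake are the related-event tables, the related components of the three safety endpoints, and the pausing criteria that depend on relatedness. Any bias would make IVIG look safer.

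**Working it through.** The plan has no figure to reproduce here. The check sets the rules side by side, counts the criteria affected, and adds one illustration on assumed inputs.

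**Step 1. Classify by onset.** Protocol 7.2.2 puts baseline assessments, randomization and first infusion on Day 1, in that order. Event recording also starts on Day 1 (Protocol 8.3.8).

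| Arm and onset | Protocol 8.3.4/8.3.8 | SAP 7.2.1 | Relatedness |
|---|---|---|---|
| IVIG, Day 1, before randomization | Not treatment-emergent | TEAE (same calendar date) | Unrelated |
| IVIG, after randomization, before infusion | Not treatment-emergent | TEAE | Unrelated |
| IVIG, after infusion starts | Not excluded | TEAE | Assessed |
| SMT alone, after randomization | Clock never starts | TEAE | Not assessed |

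The first, second and fourth rows show the conflict.

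**Step 2. Add worsening.** Suppose, as an invented example, that a creatinine of 2.5 mg/dL is recorded as an adverse event after consent and before infusion, and reaches 4.5 mg/dL on Day 3. Nothing forbids a second record. The broad definition in 8.3.3.1 and the rule in 8.3.8 on clinically significant laboratory abnormalities would both allow one. Nothing requires it either, and several features lean towards a single record:
- 8.3.8 lists one onset, one severity and one causality entry per event and prefers related findings to be grouped under one diagnosis.
- The first causality criterion in 8.3.4 runs from administration to event onset, which a pre-infusion onset cannot satisfy.
- Change in intensity is timed only for events that occur during infusions.

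**Step 3. Related-event tables.** Tables iii, vii and ix in SAP 7.2.5 need a possible or definite rating. A single-record event is excluded from all three on either clock, because SAP 7.2.3 adopts the protocol's causality rule. On the SAP clock it still appears in the general TEAE tables.

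**Step 4. Pausing criteria in Protocol 8.5.** In listed order, with TE = needs treatment-emergence and R = needs relatedness or attribution: (1) R; (2) TE and R; (3) R; (4) TE; (5) TE; (6) TE and R; (7) TE and R; (8) the catch-all, neither.
- R: 1, 2, 3, 6, 7, so 5 of 8.
- TE: 2, 4, 5, 6, 7, so 5 of 8.
- Both: 2, 6, 7, so 3. At least one: 5 + 5 − 3 = 7.

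On the protocol clock, a single-record event can count only towards the catch-all (1 of 8). On the SAP clock it can also count towards criteria 4 and 5 (3 of 8). Section 8.5 does not say which clock it uses. The staggered start in Protocol 4.2 also depends on a definitely related SAE.

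**Step 5. Illustration of direction only.** Take 50 IVIG subjects (half of about 100). Let p be the share with a truly possibly related Grade 3 or 4 event and m the share of those forced to unrelated. Both are assumptions. The five-subject criterion is met with probability P(X ≥ 5), where X ~ Binomial(50, p(1 − m)).

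| p | m = 0 | m = 0.10 | m = 0.25 | m = 0.50 |
|---|---|---|---|---|
| 5% | 0.104 | 0.073 | 0.039 | 0.008 |
| 10% | 0.569 | 0.472 | 0.320 | 0.104 |
| 15% | 0.888 | 0.823 | 0.676 | 0.320 |

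The short window points towards small m, but the documents give neither p nor m.

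**The case against.** The strongest reply is that the documents never say worsening must stay in the old record, so the fault is an omission. That stands: the effect arises only where a site does not open a new record. But the choice is then left to each site in an open-label trial, with a text that leans towards one record.

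The second reply is that the rule reaches few events. A reader might infer that all baseline organ dysfunction aggravated by IVIG is lost, since creatinine up to just under 4 mg/dL is eligible. The documents do not support that. Conditions that predate consent are medical history or baseline findings, not events reported before infusion. The rule does not clearly catch their later worsening, which can be recorded and assessed as an event with onset after infusion. The exposed window is roughly consent to first infusion on Day 1.

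The third reply is that other safeguards exist, and they do:
- The safety committee reviews causality for all TEAEs and SAEs, and SAEs are not restricted to treatment-emergent ones.
- Under 8.3.4 the sponsor will consider the investigator's "causality assessment and also provide its own assessment".
- Two pausing criteria need no relatedness, and the catch-all needs neither label.
- Creatinine and blood pressure are summarised as change from baseline however events are coded, including at the interim analysis.

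So it would be wrong to say that such events escape the pausing rules altogether. What remains is that a non-serious event which the protocol calls non-treatment-emergent lies outside the committee's stated causality review. The plan also does not say whether the sponsor's assessment can override the fixed label or reach the tables.

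Nor does the SAP clock let events escape. It starts earlier and brings more Day 1 events into the TEAE tables. The unrelated label is what removes them from the related-event tables.

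**Conclusion.** The point holds in a limited form. The two clocks conflict on the face of the text, the protocol's clock has no meaning for SMT alone, and neither document counts worsening. Where worsening stays in the first record, an event arising between consent and first infusion is left out of three SAP tables and cannot count towards five of the eight pausing criteria. Some criteria turn on a single subject, such as one related death, so one misclassified event could matter.

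The number of such events cannot be estimated from the documents. One could assume that 10–30% of 50 IVIG subjects have a pre-infusion event and that 20–30% of those worsen, giving 50 × 0.10 × 0.20 = 1.0 to 50 × 0.30 × 0.30 = 4.5 subjects, and set that against the threshold of five. That comparison is not supported. The rates are invented, and the result counts worsening of any grade and cause, whereas the criterion needs Grade 3 or 4 events that are possibly related.

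No hypothesis test is affected, because SAP 7 plans none for safety. This is a definition worth correcting, not a defect that undermines the safety analysis as a whole.

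**What to change.** 1. Use one definition in Protocol 8.3.4 and 8.3.8 and SAP 7.2.1, for both arms: treatment-emergent means new onset, or an increase in severity or grade, after the randomization date and time. Randomization time (Protocol 4.3.2) and event onset time (8.3.8) are already collected, and the SAP's latest-possible imputation rule already covers a missing onset time.
2. Record an increase in severity, or an event becoming serious, after first exposure as a new event with its own onset, grade and causality. SMT alone has no exposure time, so there the same recording should run from randomization; otherwise the arms would be recorded differently.
3. Limit the always-unrelated label to the part of an event before exposure.
4. State in Protocol 8.5 that its criteria use this definition. The thresholds are not at issue here.

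The cost is wording in three protocol sections and one SAP section, plus a note in the CRF completion instructions. The downside is slightly more event records in both arms.
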